9.6 Data Management

All study permit approvals and access to the study data will be applied for by PPD . Application for access to individual-level data for scientific research follows a standard application procedure at the Danish and Swedish authorities. For Denmark, pseudonymized individual-level data are placed at a secure, remote server of the Danish Health Data Authority. All data analyses using the linked register data must be conducted at the server of the authority by PPD staff personally authorized by the authority under the authorisation held by PPD Solutions Denmark A/S. No other PPD staff will have access to the secure server environment. For Sweden, data from each register will be extracted by the respective register holder and delivered to PPD as pseudonymized individual-level data without unique personal identification numbers. The researchers at PPD in Denmark and Sweden will thus have access to data where individuals cannot be directly identified.

Before PPD can access the data, the data holders have collected and managed data according to their own standards. As the data contained with the national registers have been collected independently of the current study, the data collection process could not affect the research question. Once the data can be accessed, PPD will start processing the data. Each country will perform analyses with individual-level data separately as described in Section 9.7. SAS v9.4 (SAS Institute, Inc. Cary, North Carolina) or R v3.6.5 or higher (R Foundation for Statistical Computing, Vienna, Austria) languages will be used in data management for creating the analysis database, and in statistical analysis for creating tabulations and graphics, as well as in all statistical modelling. The source code of data management and data analyses is kept for inspection for five years after completion of the study (latest of final study report or first publication of study results).

According to PPD standard operating procedure, only selected study staff have rights to files and directories that contain individual-level data stored on site. Access to the individual-level study data cannot be given to any third parties; only aggregated results will be presented to the Sponsor or otherwise published. The study data cannot be used for other purposes than described in this protocol. All requests to use the study data for other purposes must be subjected to appropriate data permit processes.

PPD will maintain information on the study individuals securely on site according to up-to-date standard operating procedures. PPD will also maintain appropriate data storage, including periodic backup of files and archiving procedures. PPD will comply with procedures that include checking electronic files, maintaining security and data confidentiality, following analyses plans, and performing quality checks for all programs.

9.7 Data Analysis

Further details on the analyses corresponding to each study objective are provided in a SAP.

All analyses will be performed separately for each country. MA may be used, as appropriate, to provide summary estimates for the entire study population across both countries (see Section 9.7.3.8).

9.7.1 Analysis Sets

To address the study objectives, analysis sets will be constructed based on the study outcomes as defined in Section 9.1.2. To allow for a sufficient time period to assess the outcomes after the initiation of a stimulation cycle, the analysis sets will be restricted to outcome-specific time periods. For the analysis sets, the following outcome-specific time periods are applied: 1 year after the stimulation cycle initiation for LBR, CPR, OPR, MC-CLBR and TTLB; 1 year after the stimulation cycle and linked FET initiation for CLBR, CCPR, COPR, pregnancy loss, multiple pregnancy and treatment-associated costs; 1.5 months after the stimulation cycle initiation for oocyte retrieval and embryos cryopreserved per initiated stimulation cycle, and cycle cancellation; 1 month after the stimulation cycle aspiration for oocyte retrieval and embryos cryopreserved per aspirated stimulation cycle; 4 months after stimulation cycle initiation for OHSS; 3 months after last embryo transfer for implantation. Fresh and frozen embryo transfers will be assessed by using all fresh and frozen embryo transfers done by the end of the study period (31 December 2020).

The analysis sets and their use for the study objectives and outcomes are defined in Table 5. The use of analysis sets will be described in the statistical analysis, and any needed specific modifications or restrictions on the analysis sets needed for the analysis of the study objectives will be further described in the SAP.

Table 5. Description of analysis sets

Analysis set	Description of the analysis set	Study objective(s)	Study outcome measure(s)
Set 1	Stimulation cycles with drug of interest initiated on or before 31 December 2019	Primary objective	LBR
		Secondary objective 1	CPR
			OPR
Set 2	Stimulation cycles with drug of interest and linked FET cycles initiated on or before 31 December 2019	Primary objective	CLBR
		Secondary objective 1	CCPR
			COPR
		Secondary objective 5	Pregnancy loss
		Secondary objective 6	Multiple pregnancy
Secondary objective 9	Treatment-associated costs		
Set 3	Stimulation cycles with drug of interest initiated on or before 15 November 2020 ⁺	Secondary objective 2	Oocytes retrieved per initiated stimulation cycle
			Embryos cryopreserved per initiated stimulation cycle
			Utilizable embryos per initiated stimulation cycle
		Secondary objective 7	Cycle cancellation

Analysis set	Description of the analysis set	Study objective(s)	Study outcome measure(s)
Set 4	Stimulation cycles with drug of interest aspirated on or before 30 November 2020 ⁺	Secondary objective 2	Oocytes retrieved per aspirated stimulation cycle
			Embryos cryopreserved per aspirated stimulation cycle
			Utilizable embryos per aspirated stimulation cycle
Set 5	Stimulation cycles with drug of interest initiated on or before 31 August 2020 ⁺	Secondary objective 8	OHSS
Set 6	Fresh and frozen embryo transfers linked to stimulation cycles with drug of interest occurring on or before 31 December 2020 ⁺	Secondary objective 2	Fresh embryos transferred
			Frozen embryos transferred
Set 7	Fresh and frozen embryo transfers linked to stimulation cycles with drug of interest occurring on or before 30 September 2020 ⁺	Secondary objective 3	Implantation rate
Set 8	Women who initiated their first-ever stimulation cycle with drug of interest on or before 31 December 2019	Primary objective	MC-CLBR
		Secondary objective 4	TTLB

CCPR: cumulative clinical pregnancy rate; CLBR: cumulative live birth rate; CPR: clinical pregnancy rate; COPR: cumulative ongoing pregnancy rate; FET: frozen embryo transfer; LBR: live birth rate; MC-CLBR: multiple-cycle cumulative live birth rate; OPR: ongoing pregnancy rate; OHSS: ovarian hyperstimulation syndrome; TTLB: time-to-live birth.

Notes:

*Should data on initiated cycles from the Swedish Q-IVF be available only through 31 December 2019, this analysis set will be adjusted to the same day and month in 2019.

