The overall study period will be between 2010 and 2020. Different study period starts will be applied depending on which two drugs are being compared. For the comparison between rhFSH-alfa reference product and HP-hMG, the study period will start 1 January 2010 for both countries. This date is selected to ensure the study is sufficiently powered while also reducing heterogeneity in patient management over time. Changes that have occurred over time include moving towards vitrification rather than slow freezing for embryo cryopreservation and hence also moving from cleavage stage to blastocyst embryo transfers, elective single embryo transfers rather than double embryo transfers, and antagonist protocols rather than agonist protocols. For the comparison between rhFSH-alfa reference product and rhFSH-alfa biosimilar products, the study period will start 26 March 2014 for Denmark and 20 June 2014 for Sweden. These are the earliest dates when a rhFSH-alfa biosimilar product (Bemfola) received reimbursement status in each country. For

Sweden, where the IVF register is updated annually and has a lag time of approximately two years (see Section 9.4.2), inclusion of women undergoing IVF/ICSI treatment may end on 31 December 2019, depending on data availability at the time of data extraction. No such general restriction will be applied for Denmark, as the IVF register is updated monthly. In terms of follow-up of IVF/ICSI treatment and pregnancy outcomes, the study will end on 31 December 2020 (or last available date) for each country. Specifically, for the main analyses of the primary objective (LBR, CLBR and MC-CLBR) and secondary objective 4 (TTLB), a minimum follow-up period of 1 year has been chosen to allow sufficient time to achieve (at least) one live birth and a reasonable number of complete cycles for reliable estimates of live birth rates. Hence, the corresponding analyses are restricted to cycles initiated on or before 31 December 2019 (Sets 1 and 5 in Table 5). The minimum follow-up period will be extended to 2 years in a sensitivity analysis to explore the potential effect this has on the estimated MC-CLBR and TTLB (see sensitivity analysis 3 in Table 8).

To reduce possible bias linked to confounding by baseline characteristics, inverse probability of treatment weighting (IPTW), based on propensity scores (PS) (22), will be used to balance the distribution of potential confounders across the study cohorts.

Figure 1. Study design

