9.1.2.1 Primary

The primary outcome of this study is live birth. It is defined generally as the complete expulsion or extraction from a woman of a product of fertilization, after 22 completed weeks of gestational age; which, after such separation, breathes or shows any other evidence of life, such as heartbeat, umbilical cord pulsation or definite movement of voluntary muscles, irrespective of whether the umbilical cord has been cut or the placenta still attached or not (16).

Information on live birth will be obtained from the medical birth register in each country and the IVF register in Sweden. Only live births that can be linked to a given IVF/ICSI stimulation cycle included in the study will be considered. The live birth of multiples will be counted as one live birth in this study.

For the assessment of the primary objective and secondary objective 4, the different measures of live birth are defined as follows:

- LBR is the probability of a live birth after one initiated stimulation cycle, considering fresh embryo transfer.
- CLBR is the number of live births per initiated stimulation cycle, considering all fresh and subsequent frozen embryo transfers linked to that stimulation cycle and counting all live births from the same transfers.
- MC-CLBR is the probability of a live birth in up to five stimulation cycles, considering all fresh and subsequent frozen embryo transfers linked to each of those stimulation cycles, until the first live birth occurs.
- TTLB is the time (in number of cycles) until live birth in up to five stimulation cycles, considering all fresh and subsequent frozen embryo transfers linked to each of those stimulation cycles, until the first live birth occurs.

For the calculation of the above measures, refer to Section 9.7.3.3 (Table 7).

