3	Minimum duration of follow-up for assessment of MC-CLBR and TTLB	The main analyses of the MC-CLBR and TTLB each uses a minimum of 1 year of follow-up and includes women who had initiated their first-ever stimulation	1 year is considered sufficient to achieve at least one live birth and a reasonable number of complete cycles for reliable estimates of the MC-CLBR in view of previous studies considering up to 9 (20) and 8 (21) stimulation cycles for the estimation of cumulative live birth rates with at least 1.5 and 2 years of follow-up, respectively.	Minimum follow-up period extended to 2 years, thus restricting the analysis to women who had initiated their first-ever stimulation cycle on or before 31 December 2018.	The effect of extending the minimum follow-up period on the conservative and optimal estimates of the MC-CLBR and on TTLB will be explored. The analysis of each outcome will otherwise be repeated as described in 9.7.3.3 and 9.7.3.4.

No.	Topic	Main analysis		Sensitivity analysis	
		Method	Justification	Alteration to method	Justification
		cycle on or before 31 December 2019.			
4	CLBR	The main analysis does not consider the possible impact of oocyte yield on CLBR.	Oocyte yield is not considered in the stratified analysis.	CLBR in the first, second and third stimulation cycle will be estimated by the number of oocytes retrieved in the first cycle (cycle rank expressed as observed in the study period).	Oocyte yield is known to be positively associated with CLBR (20,40,41). The effect of oocyte yield in the first cycle will be explored for the CLBR. Otherwise the analysis will be repeated as described in 9.7.3.3 and 9.7.3.4, although rates will only be reported for the IPTW-weighted cohorts.

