the Danish National Board of Health suspected that were to some degree an under ascertainment of the true number of treatments initiated due to incomplete capture, noting that the use of electronic capture in future updates would improve quality (55,56). However, as only electronic reports are included during the period under study (2010-2020), previously identified limitations related to underreporting would not be an issue in this study. All treatment cycles and measurements on pregnancies from private and public IVF clinics are required to be reported, and the DIVF during the study period is based on electronic capture and complete and validated data (52). Similar to the Q-IVF, the DIVF has been used extensively in research (27,40,54,57,58).

As in any study assessing cumulative live birth rates of IVF treatment, uncertainty remains around end outcomes in those who discontinued treatment, had they continued. This uncertainty will be addressed by the estimation of conservative estimates and, in a sensitivity analysis, optimal estimates for the primary objective MC-CLBR outcome, based on different assumptions of live birth rates in women who discontinued treatment (see Analysis 2 in Table 8). Similarly, the impact on the conservative and optimal MC-CLBR estimates of extending the minimum follow-up to 2 years will also be explored (see Analysis 3 in Table 8).

Further, prescribing patterns of the study drugs are likely to vary to some extent across the study period. If one drug was favored over the other in the early part of the study period, the probability of observing all live births in up to five stimulation cycles using that drug would be higher than for the other one (due to availability of data with longer follow-up). Based on the feasibility assessment of the use of the study drugs in Denmark and Sweden, it is known that the use of rhFSH-alfa biosimilar products has increased gradually, with a relatively larger proportion observed during the latter part of the study period, compared with rhFSH-alfa reference product (37). Hence, it cannot be ruled out that this may lead to a downward bias for the cumulative live birth rate outcomes following COS with rhFSH-alfa biosimilar products.

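### Set 2 closes stimulations and their linked FETs on the same day, so late stimulations get little or no time for frozen transfers and CLBR can be biased downward for biosimilars

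*Protocol*

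**What the plan says.** - **Definition.** Section 9.1.2.1 defines CLBR per initiated stimulation, "considering all fresh and subsequent frozen embryo transfers linked to that stimulation cycle and counting all live births from the same transfers". No time limit per stimulation is given. Section 9.1.2.2 defines CCPR and COPR in the same way.
- **Analysis set.** Set 2, used for CLBR, CCPR and COPR, is "Stimulation cycles with drug of interest and linked FET cycles initiated on or before 31 December 2019". The abstract repeats this for CLBR.
- **Outcome period.** The text before Table 5 sets it at "1 year after the stimulation cycle and linked FET initiation for CLBR, CCPR, COPR". The year runs from the start of the FET as well, so it allows for a birth and not for reaching an FET.
- **Study starts.** For the first comparison, "For the comparison between rhFSH-alfa reference product and HP-hMG, the study period will start 1 January 2010 for both countries". For the biosimilar comparison, "the study period will start 26 March 2014 for Denmark and 20 June 2014 for Sweden".
- **Adjustment.** Table 1 (Section 9.3.2) marks calendar year of the stimulation as a baseline characteristic only, with no mark for the propensity score or for additional adjustment.
- **Sensitivity analysis.** Analysis 3 in Table 8 is headed "Minimum duration of follow-up for assessment of MC-CLBR and TTLB". CLBR is not in it.
- **Limitation.** Section 9.9.2 notes that biosimilar use grew over time and that it cannot be excluded that "this may lead to a downward bias for the cumulative live birth rate outcomes following COS with rhFSH-alfa biosimilar products".

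**The concern.** Every initiated stimulation stays in the CLBR denominator (Table 7), but a birth from FET counts only if that FET began by 31 December 2019. A stimulation begun in the last days of 2019 can contribute little beyond its fresh transfer, and if all its embryos were frozen it can contribute nothing. An early stimulation has years in which to use its frozen embryos. CLBR is modelled as a count per initiated cycle (Section 9.7.3.4), so there is no censoring to absorb the difference.

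Unequal truncation biases a comparison only if the two drugs are spread differently over calendar time. For biosimilars the protocol says they are. The artefact would then favour the reference product, which is the direction of the superiority hypothesis in Section 8, on one of the three primary measures.

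**Working it through.** **1. The plan's own figure.** From 31 December 2019 to 31 December 2020 is 366 days, which reproduces the stated one-year minimum follow-up. For CLBR that year follows the last admitted FET start.

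**2. Time available to start an FET** (31 December 2019 minus stimulation date):

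| Stimulation date | Days | Years |
|---|---|---|
| 31 December 2019 | 0 | 0 |
| 20 June 2014 (Sweden, biosimilar comparison) | 2,020 | 5.5 |
| 26 March 2014 (Denmark, biosimilar comparison) | 2,106 | 5.8 |
| 1 January 2010 (HP-hMG comparison) | 3,651 | 10.0 |

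**3. Size of the artefact with identical drugs.** The protocol gives neither FET waiting times nor uptake by year, so these inputs are assumptions:
- live birth in 22 per 100 stimulations from fresh transfer, and eventually 12 per 100 from FET;
- wait L to that FET = 0.15 y plus an exponential with mean m; total mean wait μ = 0.15 + m = 0.5, 0.8 or 1.2 y;
- period T = 5.77 y (Danish biosimilar comparison).

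The share of FET births lost is the average of P(L > time remaining) over the start dates. Ignoring a negligible tail beyond T:
- flat use: μ/T;
- use rising linearly from zero: 2μ/T − E[L²]/T², with E[L²] = m² + μ².

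For μ = 0.5: flat 0.5/5.77 = 0.087. Rising 2 × 0.0867 − 0.3725/33.29 = 0.162. Difference 0.0755 × 12 = 0.91 points.

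Numerical integration over the full period gives:

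| Mean wait (y) | Lost, flat | Lost, rising | CLBR flat, % | CLBR rising, % | Gap (points) |
|---|---|---|---|---|---|
| 0.5 | 0.087 | 0.162 | 33.0 | 32.1 | 0.91 |
| 0.8 | 0.139 | 0.245 | 32.3 | 31.1 | 1.28 |
| 1.2 | 0.207 | 0.340 | 31.5 | 29.9 | 1.59 |

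The Swedish period (T = 5.53) gives 0.94, 1.32 and 1.63.

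A moderate opposite trend gives the same gap. Here biosimilar use goes from 0.5 to 1.5 times its average while reference use goes from 1.5 to 0.5. The loss is linear in the slope, so each drug moves half the distance in opposite directions. With no difference in calendar use the gap is 0.

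**4. Other assumptions.** With a lag of 0.25 y plus an exponential of mean 0.5 to 1.5 y, 5 to 15 FET births per 100 stimulations and the same moderate trend, the gap is 0.5 to 2.3 points. For scale, Section 9.5 claims detectable differences for biosimilars of 2.5 points in Denmark and 2.0 in Sweden.

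**5. After the change.** With one FET window for all stimulations, the calendar-driven difference is 0 by construction. The share of FET births still counted is 1 − exp(−(w − 0.15)/m). For w = 1 year this is 91%, 73% and 55% at the three waits. For w = 2 years it is 99.5%, 94% and 83%.

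**The case against.** **The size is not in the protocol.** This stands. Every figure in points is conditional on assumed birth shares, waits and use patterns.

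**A larger bias might be inferred.** If reference use also falls linearly to zero by the end of 2019, the same calculation gives 1.8 to 3.2 points. The protocol does not support that pattern. Section 9.5 gives the reference product about 53% (2010-2019) and 54% (2014-2019) of stimulations in Denmark, and 36% and 35% in Sweden. These are period averages and do not exclude some decline, but they do not point to a collapse.

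**A ten-year imbalance against the later-used drug might be inferred.** The ten-year span belongs to the HP-hMG comparison, for which no use trend is documented and so no direction can be given. For biosimilars the span is 5.5 to 5.8 years.

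**Other changes over time could offset it.** Section 9.1.1 lists vitrification, blastocyst transfer, single embryo transfer and antagonist protocols. These may add to the bias or reduce it, so the net direction is not certain. It is also a reason to adjust for calendar time.

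**The protocol discloses the problem, and MC-CLBR has a longer-follow-up analysis.** Both are true, but neither changes the CLBR estimate. Analysis 5(b), restricted to 2016-2020 in Denmark, makes short-window stimulations a larger share.

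**The SAP may modify the sets.** Section 9.7.1 allows that, but the closing date is fixed in the protocol.

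**Transfers up to 31 December 2020 are used.** That sentence in Section 9.7.1 matches Set 6 (embryos transferred) and does not reopen Set 2.

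**Conclusion.** The point holds for CLBR, CCPR and COPR in the biosimilar comparison. Followed as written, the plan truncates frozen transfers unequally by calendar time. It documents that biosimilars were used later, and it fixes no adjustment or sensitivity analysis that reaches CLBR. A spurious biosimilar deficit of about 0.9 to 1.6 percentage points is plausible under the assumptions in step 3. That is a material fraction of the differences the study claims to detect. It is nil if the two drugs have the same calendar distribution. The finding is that the bias can arise, not that biosimilars are bound to show a lower CLBR. For HP-hMG the truncation is present, but the documents give no ground for a direction.

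**What to change.** 1. **Common window.** Give every stimulation the same FET window, followed by one year for birth. The rule is stimulation cutoff + FET window + 1 year ≤ 31 December 2020, or the last complete birth data in each country if earlier (Section 9.4.1 gives the Danish birth register a 13-month lag). Example: starts to 31 December 2018 and FETs within 12 months, hence by 31 December 2019, with births to 31 December 2020.
2. **Sensitivity.** Add CLBR to analysis 3 with a 24-month window and starts to 31 December 2017. The existing analysis 3 cutoff of 31 December 2018 would not do: 24 months later is 31 December 2020, which leaves the last FETs no time for a birth.
3. **Definitions.** State the window for CLBR, CCPR and COPR in the abstract, Sections 9.1.2.1 and 9.1.2.2, and Tables 5, 7 and 8. Say whether the other outcomes that use Set 2 (pregnancy loss, multiple pregnancy, costs) follow it.
4. **Adjustment.** Make calendar time of stimulation start a propensity-score covariate in Table 1. Where biosimilars were rare early on, weights may be large; Section 9.7.3.1 already provides for checking and truncating them.

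**Cost.** One year of stimulations is about 10% of the 2010 period and 17% of the Danish 2014 period (1/5.77); two years is about double. The loss falls when biosimilar use is relatively high: if use rises linearly from zero, one year removes 1 − (4.77/5.77)² = 32% of biosimilar stimulations. A 12-month window leaves 9 to 45% of eventual FET births uncounted under the waits in step 3. It also excludes most second deliveries from the same stimulation, because after a term birth from the fresh transfer only about three months remain. With identical FET timing, these losses fall equally on both cohorts.
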